1.3 Exploratory Objective

- **1.3.1** A) To prospectively evaluate and compare the sensitivity/specificity of NGS and comprehensive genomic profiling (CGP) to assess MMR gene deficiency/microsatellite instability (MSI) to standard PCR-based DNA microsatellite instability (MSI) and immunohistochemistry (IHC) testing for the identification of patients responsive to pembrolizumab. B) To evaluate the tumor mutation burden (TBN) and individual characteristics of somatic mutations identified using whole exome sequencing (WES) in ultra and hypermutated patients and their correlations to objective response, PFS and OS in pembrolizumab-treated patients.
- **1.3.2** To explore the composition of immune infiltrates in POLE/POLD1 and MMR defective tumor specimens/biopsies from primary and/or metastatic/recurrent sites with selected markers including (but not limited) to CD4+,CD8+, FoxP3, CD25, LAG-3, TIM-3, and ICOS and their correlations to objective response, PFS and OS in pembrolizumab -treated patients.
- **1.3.3** To systematically evaluate PD-1 and B7-H1 (i.e., PD-1 Ligand) expression in tumor infiltrating lymphocytes (TILs) and tumor cancer cells and explore their correlations with objective response, PFS, and OS in pembrolizumab -treated patients with PD-1 and B7-H1 scoring results.

1.3.4 To explore the association with treatment and subject response in peripheral blood populations in ultramutated and hypermutated patients before and during pembrolizumab treatment, including absolute lymphocyte counts, number of T cells, T-cell subsets, NK cells, and B cells as well as their cellular phenotypes by flow cytometry.

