
Recent data from immune check point inhibitors immunotherapy trials **in melanoma patients** have hypothesized that the mutational burden of the tumor may play a critical role for the identification of patients most likely to respond to immunotherapy. Consistent with this view, in these studies the mutational burden was higher in melanoma patients experiencing a sustained clinical benefit than in those without a sustained benefit (8). In this regard, because only a tiny proportion of predicted neo-epitopes are actually presented on the cell surface with MHC and are targets of endogenous T cell responses, it is likely, that the number of predicted

mutation-associated neoantigens is proportionate to the number of actual mutation-associated neoantigens, and tumors with a high number of actual mutation-associated neoantigens are more likely to stimulate the immune system to react against the tumor (8). These recent data strongly suggest that the presence of a specific threshold of mutations in hyper-mutated endometrial cancer patients may be potentially critical for the identification of patients experiencing maximal/sustained clinical benefit to immune check point inhibitors. Consistent with this view, as shown in Figure 2 below for the 65 MMR gene defective endometrial carcinoma cases studied in the TCGA report, (reference # 2, data downloadable from the TCGA online resource: https://tcga-data.nci.nih.gov/tcga/), hypermutated tumors varied greatly in the number of total mutations.

Figure 2. Density plots of the MSI hypermutated endometrial carcinoma patients from TCGA (ref. 2). We divided the MSI hypermutated original category, composed of n=65 patients in two sub-categories: 1) MSI MMR-defective secondary to MLH1 promoter methylation without mutations in MMR genes (ie, 52 patients: Panel A) and 2) MSI MMR-defective with at least one mutation in one of the 4 MMR genes (ie, 13 patients: Panel B). We found **MSI high patients with MMR gene mutations to harbor a 2.39 folds higher number of mutations (mean mutation number = 1404 vs 587, respectively) when compared to MSI high MLH1 promoter methylated patients.**

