Accordingly, to evaluate whether a specific threshold of mutations is necessary to induce a response and/or whether in addition to the number, a specific signature of DNA mutations (for example a high prevalence of C:G>G:C transversions or enrichment with two separate signatures [TCT \rightarrow A] and [TCG \rightarrow , i.e., typical of POLE exonuclease mutations) is necessary to trigger strong pembrolizumab immune responses, we are planning to perform whole exome sequencing (WES) in all patients selected by NGS and CGA and treated with pembrolizumab within the clinical trial.

In this regard, because pre-existing immunity is present in a significant subset of endometrial cancer patients and because tumor infiltrating lymphocytes (TIL) are often suppressed by the PD1/PD-1L axis the use of Pembrolizumab may be highly effective in re-invigorating pre-existing immunity in this selected cancer patient population. Consistent with this view, compelling evidence indicates that B7 molecules (i.e., B7-1/CD80, B7-2/CD86, B7-H1/PDL1, B7-H2/L-ICOS, B7-DC, B7-H3 and B7-H4) and their ligands (i.e., CTLA-4, CD28, PD-1, ICOS) not only provide crucial positive signals to stimulate and support T-cell activation, but can also offer negative signals that control and suppress potentially protective T-cell responses against spontaneously arising and virally-induced human tumors (20). Expression of these molecules on the surface of endometrial tumor cells, tumor associated macrophages (TAM) and/or DC, may attenuate or abrogate the ability of the immune system to successfully eliminate strongly antigenic (i.e., hypermutated and ultramutated) tumors (20). Because these negative signals in multiple human solid tumors have been shown to be largely provided by PD-1 or programmed death-1, blockade of PD-1/PD-L1 co-inhibitory pathways by novel monoclonal antibodies may represent an

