11.7 Exploratory Hypothesis and Endpoints

Dot plots and box plots in conjunction with Spearman's correlation analysis will be used to explore the associations of tumor expressions of PD-L1, PD-1, lymphocyte infiltration and other interesting biomarkers (such as CD4+,CD8+, FoxP3, CD25, LAG-3, TIM-3, and ICOS) with the ordered RECIST categories of tumor response. Logistic regression will be used to explore associations of the same tumor expressions and biomarkers with OR. Cox proportional-hazards (PH) regression will be utilized to evaluate the associations of these tumor expressions and biomarkers with PFS and OS.

The above analysis approaches will also be used to evaluate the effects of TBN and individual somatic mutations at baseline on RECIST response, OR, PFS, and OS. The effect on PFS and OS of TBN and individual somatic mutations that accumulate during treatment will be analyzed using either landmark analysis (25) or Cox regression with time-dependent covariates.

The sensitivity and specificity of NGS and CGP to assess MMR gene deficiency/MSI will be assessed using standard contingency-table methods with the gold standard being PCR-based DNA MSI-testing. Agreement between methods will also be assessed using Cohen's Kappa in conjunction with McNemar's test to test for systematic bias in the disagreements that occur.

The association of peripheral blood populations (absolute lymphocyte counts, number of T cells, T-cell subsets, NK cells, and B cells, as well as cellular phenotypes) with treatment and subject response will be explored using profile plots versus treatment cycle, in conjunction with longitudinal-analysis techniques such as mixed-models analysis or regression with generalized estimating equations to accommodate the non-independence among multiple measurements from the same subject over time.

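### Section 11.7 specifies no adjustment for total mutation burden when individual mutations are related to response, PFS and OS, so it cannot show whether a mutation matters beyond the number of mutations

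*Combined protocol and SAP*

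**What the plan says.** Exploratory objective 1.3.1 B is to "evaluate the tumor mutation burden (TBN) and individual characteristics of somatic mutations identified using whole exome sequencing (WES") and to relate both to objective response, PFS and OS. Section 11.7 sets out the methods, first for protein and immune markers: Spearman correlation with ordered RECIST category, then "Logistic regression will be used to explore associations of the same tumor expressions and biomarkers with OR", then "Cox proportional-hazards (PH) regression will be utilized to evaluate the associations of these tumor expressions and biomarkers with PFS and OS". It says the same approaches will be "used to evaluate the effects of TBN and individual somatic mutations at baseline on RECIST response, OR, PFS, and OS". It names no covariate and no model holding burden and a mutation together, and no other section supplies one.

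Section 2.1 Background gives three relevant statements.
- On burden and benefit, it reports that "the mutational burden was higher in melanoma patients experiencing a sustained clinical benefit than in those without a sustained benefit" and argues that "tumors with a high number of actual mutation-associated neoantigens are more likely to stimulate the immune system to react against the tumor".
- On the spread of burden among MSI-hypermutated tumours, it compares those with an MMR gene mutation (13 of 65) and those with MLH1 promoter methylation (52 of 65): "mean mutation number = 1404 vs 587, respectively".
- On the question behind the sequencing, it asks whether a threshold of mutations is needed and "whether in addition to the number, a specific signature of DNA mutations".

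Whole exome sequencing is planned for all treated patients (sections 2.1 and 5.0), so burden will be available wherever an individual mutation is.

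**The concern.** Burden can act as a common cause. The more mutations a tumour carries, the likelier it is to carry any particular passenger. If burden also makes response more likely, an inert passenger is associated with response simply because it marks a high-burden tumour. The error has the same sign for every such gene, so it does not average out across a gene list. It would look like a coherent set of predictors.

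Asking whether something matters in addition to the number of mutations means holding the number fixed, and marginal tests do not do that. What is at stake is the product of this exploratory work, a list of candidate mutations for later study. The two-stage decision, the safety endpoint and the PFS and OS descriptions are not affected.

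**Working it through.** **The plan's own figure.** 1404 / 587 = 2.39, as section 2.1 states. The shares are 13/65 = 20% and 52/65 = 80%. The documents give no operating figure for the mutation analysis itself.

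**Step 1: how carriage follows burden.** Model the chance of carrying a given passenger as 1 - exp(-c x burden), and assume 25% carriage at 587 mutations.
- At 1404 mutations: 1 - 0.75^2.39 = 50%.
- At an assumed 5000 mutations (ultramutated): 1 - 0.75^(5000/587) = 1 - 0.75^8.52 = 91%.

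**Step 2: a hand calculation.** Use only the two groups with no spread inside them, an overall response rate of 25% (the design alternative) and an assumed odds ratio of 2 per doubling of burden. The between-group odds ratio is then 2^log2(2.39) = 2.39. Solving 0.8p + 0.2q = 0.25 with that odds ratio gives p = 21.4% (low burden) and q = 39.4% (high burden).
- Carriers: 0.8 x 0.25 + 0.2 x 0.497 = 0.299 of patients. Response among them = (0.200 x 0.214 + 0.0995 x 0.394) / 0.299 = 27.4%.
- Non-carriers: 0.701 of patients. Response = (0.600 x 0.214 + 0.1005 x 0.394) / 0.701 = 24.0%.
- Marginal odds ratio = (0.274/0.726) / (0.240/0.760) = 1.20, for a mutation with no effect.

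Spread of burden within the groups raises this figure.

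**Step 3: logistic regression with within-group spread.** Simulation with N = 25, the 80/20 mixture and 30% average carriage. Assumed: log-SD of burden 0.3 to 1.0, odds ratio 2 or 4 per doubling, response rate 25% or 50%.

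| Inert passenger | Unadjusted | With log2 burden |
|---|---|---|
| Odds ratio, burden affects response | 1.3 to 4.3 (population) | 0.87 to 1.05 (average Firth estimate) |
| False positives, Firth Wald, nominal 5% | 1-22% | 0.2-1.8% |
| False positives, Fisher, nominal 5% | 3-24% | not applicable |

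With no burden effect, the unadjusted population odds ratio is 1.0 and false positives are 1.6% (Wald) or 2-3% (Fisher). These tests are conservative at this sample size.

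**Step 4: Spearman against ordered RECIST category.** Simulation with n = 24 and the same mixture. Assumed: log-SD 0.3-0.5, odds ratio 2-4.5 per doubling. Adjustment is partial Spearman given burden rank.

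| Scenario | Unadjusted | Adjusted |
|---|---|---|
| No ultramutated patient | 6-14% | about 5% |
| Two ultramutated patients (assumed 5000 mutations each) | 11-28% | about 5% |
| Burden has no effect | about 5% | about 5% |

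Where burden matters, most false signals point towards better response. Where it does not, they split about evenly.

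Two ultramutated patients is a plausible number. Section 2.1 gives 2% ultramutated and 24% hypermutated among recurrences in the cited trial, and 2/26 x 24 = 1.8.

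PFS and OS were not simulated. The same direction of bias is expected there.

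**The case against.** **Silence is not a decision.** Section 11.7 does not say the tests will be unadjusted, and logistic and Cox models can take burden as a covariate. This stands. But Spearman correlation, as named, has no place for a covariate, and for the other two models the choice would be made after the data are seen.

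**The bias is conditional.** Section 2.1 draws on melanoma studies and puts the role of burden as a hypothesis. Whether burden matters in these patients is itself part of the objective. If it does not, there is nothing to correct. This stands, and it is a reason to show both results.

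**The in-addition question is about signatures.** Those words in section 2.1 concern a mutational signature, and objective 1.3.1 B does not use them. A signature measured as a proportion of mutations is not raised mechanically by burden as carriage of a gene mutation is. The simulations cover carriage only. This also stands, but section 11.7 does analyse individual mutations.

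**The size depends on outside assumptions.** Within-group spread matters most. At log-SD 1.0, with no ultramutated patient, the unadjusted Spearman rate was 16-33%. The shares and means come from the genome atlas series, not from trial patients.

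**Stronger readings.** A reader might infer that any passenger mutation will look predictive. The rates above contradict that: in the Spearman scenarios of step 4, at least 72% of inert mutations are not flagged even in the worst case. A reader might also multiply these rates by a number of genes to get a count of false findings. The documents give no number of genes to be tested, and such a count would mix confounding with multiplicity, a separate gap.

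**Adjustment is fragile here.** At 25% response, 22-25 patients give 5.5-6.25 responders. In one check, 11-21% of two-covariate logistic fits were separated, against 10-18% with the mutation alone. Ordinary maximum likelihood is therefore unsafe with or without burden, which argues for penalised models.

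**Conclusion.** The point holds in a limited form. Section 11.7 specifies no burden adjustment for individual mutations, and marginal tests cannot separate a mutation's own association from that of burden. If burden affects outcome, estimates for inert passengers are biased in one direction. Under the assumptions of step 4, false positives run at about 6-14% with no ultramutated patient and 11-28% with two, against about 5% after adjustment. For logistic regression the inert mutation's odds ratio is about 1.3-4.3 unadjusted and close to 1 adjusted. There is no inflation if burden has no effect.

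The odds ratio per doubling, the within-group spread, the carriage rates and the ultramutated burden are assumptions; the 587 and 1404 means and the 80/20 split are the protocol's. Exploratory status excuses low power, but it does not remove a foreseeable bias that a covariate already being measured can address.

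**What to change.** In section 11.7, state that each individual-mutation association will be reported twice, unadjusted and adjusted for total burden, and labelled hypothesis-generating:
- RECIST category: partial Spearman given burden rank.
- Objective response: Firth-penalised logistic regression with log2 burden as a covariate.
- PFS and OS: Firth-penalised Cox regression with log2 burden as a covariate.
- POLE/POLD1 and MMR genes: these generate the burden, so adjustment would remove part of their effect. Keep the unadjusted result as main and label the adjusted one as the effect beyond burden.

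The cost is SAP wording and penalised software; no new data are needed. The downside is lost precision for genes closely tied to burden, and sparse models with about 6 responders expected at a 25% response rate. Adjusted results will often be inconclusive and should be reported as such.

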2.0 BACKGROUND & RATIONALE

2.1 Background

Endometrial cancer is the most common gynecologic malignancy with approximately 54,870 new cases and 10,170 estimated deaths related to the disease in the United States annually (1). Recently, using a comprehensive genetic investigation, The Cancer Genome Atlas (TCGA) Research Network provided compelling evidence that endometrial cancers result from heterogeneous somatic mutations and classified endometrial cancers into four categories: 1) polymerase epsilon (POLE)-ultramutated, 2) microsatellite instability hypermutated (MMR-defective), 3) copy-number low and 4) copy-number high, serous-like (2). In this landmark study, patients harboring POLE-ultramutated (7%) were found to have the best prognosis (Figure 1 Left panel below and reference #2). After the initial TCGA report, multiple studies from our group as well as others have confirmed that despite commonly being of high histological grade, ultra/hyper-mutation is correlated with a more favorable prognosis in both Type I and Type II endometrial cancer patients (3-6). Unfortunately, however, as recently demonstrated by the whole exome sequencing (WES) of 243 patients with endometrial disease enrolled in GOG86P (Figure 1 below, right panel, ref. # (7) and [name] MD personal communication) over 25% of patients developing recurrence, which was fatal in the majority of the cases, harbored an ultramutated or hypermutated tumor phenotype. Novel, effective treatment options for ultramutated and hypermutated recurrent endometrial cancer patients remain therefore desperately needed.

Figure 1. Molecular stratification of 232 WES endometrial cancer patients (TCGA report, left Panel, ref. #2) vs 243 endometrial cancer patients with recurrent disease sequenced using WES enrolled in GOG 86P (right panel, ref#7). In GOG86P patients with ultramutated and hypermutated tumors accounted for 2% and 24% of all recurrences, respectively.

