Endometrial cancer with a MSI phenotype may occur secondary to different genetic events such as germline mutations in one of the MMR genes (as observed in patients with Lynch syndrome) or because of epigenetic silencing of the promoters of both alleles of the MLH1 gene. Moreover, another group of tumors with MSI phenotype (also referred as "Lynch like" tumors) exist that exhibit loss of expression of 1 or more of the MMR genes secondary to somatic mutations. Accordingly, PCR-based MSI and/or IHC testing are currently used in the clinic to identify tumors with mismatch repair gene defect. However, both MSI and IHC may have a 10-15% false negative rate. In addition the sensitivity of MSI testing for the identification of MSH6 mutated patients (ie, a mutation more prevalent in hyper-mutated endometrial cancer when compared to colon carcinoma) can be as low as 55% (15-17). These data imply that a significant number of endometrial cancer patients harboring hyper-mutated tumors potentially eligible to pembrolizumab may be missed using standard MSI testing because associated with a positive IHC staining and/or displayed low or no MSI by standard PCR testing (15-17). With the goal to overcome the current limitations in the identification of endometrial cancer patients potentially responsive to immunotherapy, in collaboration with FM (Foundation Medicine, Inc. Cambridge, MA) we recently developed and validated a novel computational method to assess microsatellite instability (MSI) and tumor mutation burden (TMB) using next generation sequencing (NGS) data and applied it to a series endometrial carcinoma (EA) patients assayed with comprehensive genomic profiling (CGP)(18,19). Briefly, DNA was extracted from 257 FFPE EA clinical specimens and CGP was performed on hybridization-captured libraries of 315 cancer-related genes plus 47 introns from 19 genes frequently rearranged in cancer. 114 intronic homopolymer repeat loci (10-20bp long in the human reference genome) were analyzed for length variability and compiled into an overall MSI score via principal components analysis. Predictions of MSI-H (High) or MSS (MSI-Stable) and tumor mutation burden (TMB) were validated against colorectal and EA in which MSI status was previously determined by PCR or IHC (ie, current standards), showing an overall concordance of 97% (65/67). Importantly, NGS and assessment of tumor MSI status by CGP was able to detect 3 times as many patients who may potentially benefit from immunotherapy (i.e., hyper-mutated) compared to genomic alteration in MMR pathway genes alone, while simultaneously detecting POLE ultra-mutated and hyper-mutated MMR gene-defective MSI stable endometrial cancer patients (18,19).

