2.2 Rationale

2.2.1 Rationale for the Trial and Selected Subject Population

Because POLE/POLD1-ultra-mutated and/or hyper-mutated/MMR-defective endometrial tumors harbor a large number of novel mutations and are heavily infiltrated with TIL, anti-PD1 therapy with Pembrolizumab may represent an ideal treatment option for these patients to re-invigorate pre-existing immune responses and eliminate residual/recurrent chemotherapy and radiation resistant disease.

The use of a well validated next generation sequencing (NGS) method (Foundation Medicine, Inc. Cambridge, MA)(18,19)(ie, the test is already standardized and performed in CLIA-certified laboratories without need for assay development) that allows assessment of tumor mutation burden (TMB) followed by a comprehensive genomic profiling analysis (CGP)(18,19) may represent the ideal approach to identify the population of ultramutated (i.e., POLE-mutated MSI stable) and hyper-mutated (i.e., MMR-defective MSI High, MSI low and MSI stable) patients most likely to respond to pembrolizumab therapy. Moreover, the use of comprehensive whole exome sequencing (WES) in the patient populations selected for pembrolizumab treatment by FM testing will allow a direct correlation of the total number and the characteristics of the individual mutations identified in these patients with clinical responses to the immune check point inhibitor.

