- 1) To prospectively evaluate and compare the sensitivity/specificity of NGS and comprehensive genomic profiling (CGP) to assess MMR gene deficiency/microsatellite instability (MSI) to standard PCR-based DNA microsatellite instability (MSI) and immunohistochemistry (IHC) testing for the identification of patients responsive to pembrolizumab. B) To evaluate the tumor mutation burden (TBN) and individual characteristics of somatic mutations identified using whole exome sequencing (WES) in ultra and hypermutated patients and their correlations to OR, PFS and OS in pembrolizumab-treated patients.
- 2) To explore the composition of immune infiltrates in POLE/POLD1 and MMR defective tumor specimens/biopsies from primary and/or metastatic/recurrent sites with selected markers including (but not limited to) CD4+,CD8+, FoxP3, CD25, LAG-3, TIM-3, and ICOS and their correlations to OR, PFS and OS in pembrolizumab -treated patients.

- 3) To systematically evaluate PD-1 and B7-H1 (i.e., PD-1 Ligand) expression in tumor infiltrating lymphocytes (TILs) and tumor cancer cells, and explore their correlations with OR, PFS, and OS in pembrolizumab -treated patients with PD-1 and B7-H1 scoring results.
- 4) To explore the association with treatment and subject response in peripheral blood populations in ultramutated and hypermutated patients before and during pembrolizumab treatment, including absolute lymphocyte counts, number of T cells, T-cell subsets, NK cells, and B cells as well as their cellular phenotypes by flow cytometry.

Primary Objectives Study Design

Primary Hypothesis and Endpoints

Primary Hypothesis:

The intent of this study is to evaluate the efficacy of the study regimen measured by objective tumor response. Tumor response is dichotomized as response (i.e., complete or partial response) vs. non-response (i.e., stable disease, progressive disease, or indeterminate disease) and is assumed to have a Bernoulli distribution with a probability equal to π . Given a sample size, the number of tumor responses is binomially distributed with a given sample size and probability equal to π . Statistically, the evaluation of the study regimen efficacy measured by tumor response will be formulated through hypothesis testing via tumor response.

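### Section 11.7 scores NGS/CGP against PCR-MSI as the gold standard although section 2.1 says PCR-MSI misses cases, and it never relates test status to response

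*Combined protocol and SAP*

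**What the plan says.** Objective 1.3.1A compares NGS/CGP with standard testing "for the identification of patients responsive to pembrolizumab". Section 11 repeats the aim and names both comparators: "standard PCR-based DNA microsatellite instability (MSI) and immunohistochemistry (IHC) testing for the identification of patients responsive to pembrolizumab".

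Section 11.7 gives the method. The sensitivity and specificity of NGS and CGP for MMR deficiency/MSI "will be assessed using standard contingency-table methods with the gold standard being PCR-based DNA MSI-testing". Cohen's kappa and McNemar's test are added for agreement and for the direction of disagreement.

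The background describes PCR-MSI as fallible. Section 2.1 states that "both MSI and IHC may have a 10-15% false negative rate" and that "the sensitivity of MSI testing for the identification of MSH6 mutated patients" can fall to 55%. It credits NGS/CGP with finding more patients than MMR gene alterations alone, "while simultaneously detecting POLE ultra-mutated and hyper-mutated MMR gene-defective MSI stable endometrial cancer patients". Section 2.2.1 wants the assay to pick out hypermutated tumours whatever their MSI result: "MMR-defective MSI High, MSI low and MSI stable) patients most likely to respond to pembrolizumab therapy".

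For outcome, section 11.7 relates PD-L1, PD-1, lymphocyte infiltration, other immune markers, TBN, individual somatic mutations and blood populations to response; all but the blood populations are also related to PFS and OS. It does not name NGS, PCR-MSI or IHC status in any of these analyses. IHC is not mentioned there by name.

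**The concern.** A gold standard is taken as true. Against PCR-MSI, every NGS-positive, PCR-negative tumour is an NGS false positive, and no result could show NGS to be better than PCR. Yet these are the tumours that NGS is meant to add: sections 2.1 and 2.2.1 justify its use by the patients whom standard testing misses.

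The objective also asks which test finds patients who respond. A table of one test against another cannot answer that, and no other analysis in section 11.7 takes test status as the predictor. The aim could therefore end with an apparent specificity that counts the expected gain as error and does not show whether the extra patients benefited.

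The population matters too. Sections 3.2.3 and 3.5 allow entry by NGS/CGP or by standard testing. A table of treated patients is thus conditional on a qualifying result and holds few tumours negative on both tests. A table of everyone tested would hold many. Section 11.7 does not say which is meant.

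**Working it through.** **The documents' own figure.** Section 2.1 reports concordance of NGS MSI calls with PCR or IHC: 65/67 = 97.0% (exact 95% interval 89.6-99.6%). It reproduces. Discordance was 2/67 = 3.0%, in a sample that included colorectal tumours and whose case mix is not given.

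**Inputs from the documents.** PCR miss rate f = 10-15% (section 2.1). Maximum accrual 25 (section 11.3). Case mix from the Figure 1 legend: "ultramutated and hypermutated tumors accounted for 2% and 24% of all recurrences, respectively".

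**Assumptions not in the documents.** NGS makes no error, PCR has no false positives, and the recurrence shares apply to the patients tested. The table concerns MMR deficiency/MSI, so a POLE-only tumour is negative on both tests.

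**Notation.** a = positive on both; b = NGS+/PCR-; c = NGS-/PCR+ = 0; d = negative on both. Apparent NGS sensitivity = a/(a+c) = 100%. Apparent NGS specificity = d/(b+d). Kappa = (Po - Pe)/(1 - Pe).

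**(a) Treated patients, N = 25.** Expected POLE-only count: 25 x 2/(2+24) = 1.92, taken as 2, with 1 and 3 as a range. Then b = (25 - d) x f.

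| d | f | b | Specificity | Kappa |
|---|---|---|---|---|
| 1 | 0.10 | 2.40 | 1/3.40 = 29.4% | 0.419 |
| 1 | 0.15 | 3.60 | 1/4.60 = 21.7% | 0.312 |
| 2 | 0.10 | 2.30 | 2/4.30 = 46.5% | 0.590 |
| 2 | 0.15 | 3.45 | 2/5.45 = 36.7% | 0.476 |
| 3 | 0.10 | 2.20 | 3/5.20 = 57.7% | 0.684 |
| 3 | 0.15 | 3.30 | 3/6.30 = 47.6% | 0.576 |

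Kappa for d = 2, f = 0.10: a = 20.7; Po = 22.7/25 = 0.908; Pe = 0.92 x 0.828 + 0.08 x 0.172 = 0.7755; kappa = 0.1325/0.2245 = 0.590.

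With no POLE-only tumour, d = 0 and apparent specificity is 0%. In whole patients, 3 NGS+/PCR- and 2 negative on both gives 2/5 = 40%, exact 95% interval 5-85%.

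**(b) Unselected tested population.** Per 100 patients, 24 are MMR-defective and 76 negative on both. For f = 0.10, b = 2.4, specificity 76/78.4 = 96.9%, kappa 0.932. For f = 0.15, b = 3.6, specificity 76/79.6 = 95.5%, kappa 0.896.

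NGS is error-free by assumption in both settings, so its true specificity is 100%. The gap between (a) and (b) comes only from the population.

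**What kappa and McNemar add.** They show how much the tests disagree and in which direction, not which is right. They also have little power here: with all discordant pairs one way, exact two-sided McNemar p = 2 x 0.5^b, which is 0.25 for 3 pairs, 0.125 for 4 and 0.031 for 6.

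**The case against.** The strongest defence is that the mention of responsive patients states the purpose of the tests, not the reference condition. The target would then be MMR deficiency/MSI, as section 11.7 words it, and scoring a new assay against current clinical practice is conventional. That reading is possible. It supports reporting agreement with PCR, but not treating PCR as true after stating that it misses cases. Under it, the NGS+/PCR- tumours are still counted as errors.

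Kappa and McNemar would make an excess of NGS+/PCR- results visible. That is so, but they cannot say whether the excess is gain or error.

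The response analyses include somatic mutations, and the biomarker list is open-ended. But those mutations belong to objective 1.3.1B, by whole exome sequencing, and the markers listed as examples are immune markers. The exact statement is that test status is not named in section 11.7.

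The objections to the size have more force. Setting (a) implies discordance of 2.30/25 = 9.2% to 3.45/25 = 13.8%, against 3.0% in the reported validation; setting (b), at 2.4-3.6%, is close to it. The validation sample was not selected as treated patients are, so this does not refute (a), but it does make 37-47% an illustration and not a forecast. The figure also turns on an assumed count of two POLE-only tumours and does not model entry route: patients who enter by standard testing would seldom be NGS+/PCR-.

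Finally, section 5.0 plans both kinds of testing on required specimens, and the objective points towards treated patients. The population point taken alone is therefore a clarification.

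**Conclusion.** The concern holds and is minor. The inconsistency lies in the text and needs no assumption: section 11.7 takes as truth a test that section 2.1 says misses MMR-defective tumours, and it names no analysis of test status against response.

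The size is conditional on the assumptions listed with the calculation. An error-free NGS assay could show a specificity of about 40% in treated patients or about 96% in everyone tested. In the second setting the distortion is small. In the first it ranges from 22% to 58% as the number of POLE-only tumours goes from 1 to 3. Confidence is high in the inconsistency and lower in any particular figure. One exploratory aim is affected; the primary and secondary analyses, sample size and error rates are not.

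**What to change.** Change section 11.7 in three places.

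1. Remove the gold-standard designation and state that NGS+/PCR- results are not read as NGS errors. Report the pairwise cross-tabulations of NGS/CGP, PCR-MSI and IHC as agreement only, keeping kappa and McNemar. Percent agreement against PCR has the same values as the present sensitivity and specificity, so what changes here is the interpretation.
2. Add objective response by test pattern (NGS+/PCR+, NGS+/PCR-, NGS-/PCR+, both negative, and likewise with IHC) with exact 95% intervals, labelled descriptive.
3. Name the analysis population. If it is treated patients, say that the estimates are conditional on entry by at least one positive test. If it is everyone tested, say that both kinds of test are needed in each patient, because section 3.5 allows entry testing by either route.

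The cost is SAP wording and one extra table. For treated patients the data are already planned: section 5.0 provides for NGS/CGP, PCR and IHC, and response is the primary endpoint. The table will be imprecise. With 3 NGS+/PCR- patients, the exact 95% interval for response is 0-71% if none respond and 29-100% if all do. It cannot settle the question alone, and sensitivity and specificity for response in the whole tested population stay out of reach because only test-selected patients are treated.
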